10.4 Secondary outcomes

Post-prandial plasma:

1. AUC for total IAA concentration
2. AUC leucine (anabolic trigger for protein synthesis)
3. AUC lysine (first limiting amino acid)
4. Insulin
5. Glucose

Sensory analysis in response to the meals using linear Likert scales postprandial. This will be measured at 0 minutes preprandial and 30, 90, and 240 minutes postprandial.

11 STUDY DESIGN

11.1 Type of Study

A randomized controlled trial with a crossover design (cRCT) comprising three arms in a clinical laboratory setting.

11.2 Subjects, groups, and centres

This study will recruit 8 older male and female participants (67-77 years of age; BMI ≥ 23 to ≤ 30 kg/m²). Participants will be recruited from the local Auckland community via general advertisement at the University, University participant databases, social media, community notice boards, web pages, and word of mouth.

The study will be a single-center, lab-based study.

Dropouts, that is, participants who start and do not complete, are predicted from several levels:

1. Illness
2. Unexpected life events

With the estimated sample size of 8 participants, the conservative target recruitment into the study (working backward) should be 10 (25% dropout) based on recent experience. Participants who withdraw will be replaced with two analyses available: full dataset (includes any partially completed participants) and per Protocol.

11.3 Expected study duration and milestones.

Participant recruitment and commencement of the study will be approximately 30th July 2023 and will proceed until complete. All data collection is anticipated to be completed by 15th April 2024. Sample analysis is anticipated to be completed by Nov 2024. Statistical analysis and write up early 2025. The analysis components will continue (stated Feb 2023 with the preparation of plasma amino acid assay) and continue during data collection through total and stable-isotopically labelled amino acid assay, with samples run in batches to cluster between-run variability.

- October to November 2023 – study protocol development and organization.
- November 2023 to January 2024 – study protocol submission to the ethical committee.
- November-May 2023-24 - recruitment period.
- Late February 2024 to October-2024 - testing/data collection period.
- 1st October to late 2024 - data analysis, manuscript/thesis chapter preparation, and reporting.

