12.5 Subject withdrawal criteria

The study participants are entitled to withdraw from the study at any time voluntarily and for any other reason without affecting their access to the treatment or their future treatment by the Investigator. In addition, a participant may be withdrawn from the study at any time for reasons including, but not limited to, the following:

- Investigator's medical decision when continuing the study would compromise the safety of the participant.
- The participant is unwilling or unable to adhere to protocol requirements.
- In the event of injury.
- Non-compliance with the dietary intervention protocols (pre-intervention control diet and interventional diet).
- Observation of adverse effects.
- Absence from more than two testing sessions.

Participants will be notified by the Investigator prior to withdrawal from the study/investigational product in writing with a full explanation for their withdrawal. Depending on the time of withdrawal from the study protocol, participants will be followed up as follows:

- Prior to or following participation in any trials, participants will be provided standard notification of reasons for withdrawal.
-

- During the trials, participants will be withdrawn following non-compliance to the interventional diets, inability to maintain a normal diet and allowed physical activity patterns, or any observed adverse effect. Participants' condition will be monitored for 24 hours following withdrawal if due to adverse effects.

Participants withdrawn during the study will be replaced in randomized sequence order until n=8 is complete or a maximum dropout replacement of 2 is met or exceeded.

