16 CONDUCT OF THE STUDY

16.1 Subject recruitment

A total of 8 men and women (67-77 years of age) will be required to complete the study, with contingency for another 2 if required due to dropout. The target is 4 in each gender, with contingency to complete 5 and 3 of either gender combination, depending on recruitment. Participants will be recruited from the local Auckland community via general advertisement at the University, University participant databases, social media, community notice boards, web pages, and word of mouth. Each participant will have the study outline and requirements explained in detail. At this point, they will be allowed to ask questions regarding the study and answer a health questionnaire. An inclusion checklist will be completed after the subject has agreed to participate by signing the consent. Subjects will be enrolled after fulfilling all inclusion criteria and presenting none of the exclusion criteria.

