18.2 Sample size calculations

The sample size was determined from the only relevant available NB data of Kim et al., 2018 where the egg vs. cereal difference (expected effect size between no and excellent quality) was 7 g net protein accretion in 165 min of infusion time, and the standard error derived from the p-value of 1.53 g (Kim et al., 2018). With the smallest important change of 2.2 g protein, using traditional null hypothesis significance testing with 5% type-1 and 20% type-2 error rates, a sample size of 8 was required (Hopkins, 2006), which we felt provided sufficient precision for the 30% of the anticipated difference between high and excellent protein quality, relative to the no quality contrast.

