18.5 Datasets to be analysed

18.5.1 *Full analysis dataset*

All participants provided at least 2 complete treatments.

18.5.2 *PP analysis dataset*

All participants providing a full set of 3 treatments finished.

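### Recruiting 10 to obtain 8 completers covers 20% dropout, not the 25% stated in section 11.2; the shortfall is one participant.

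*Protocol*

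**What the plan says.** Section 11.2 starts from the target, "With the estimated sample size of 8 participants", and then sets recruitment: "the conservative target recruitment into the study (working backward) should be 10 (25% dropout) based on recent experience". Just before that it says who counts as a dropout: "Dropouts, that is, participants who start and do not complete, are predicted from several levels".

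Two other sections set the room for replacement. Section 16.1 says that 8 men and women "will be required to complete the study, with contingency for another 2 if required due to dropout". Section 12.5 says that withdrawn participants will be "replaced in randomized sequence order until n=8 is complete or a maximum dropout replacement of 2 is met or exceeded".

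The 8 comes from section 18.2: "with 5% type-1 and 20% type-2 error rates, a sample size of 8 was required". Section 18.5 defines two analysis sets. The per-protocol set needs all three treatments. The entry for the full analysis set reads "All participants provided at least 2 complete treatments".

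**The concern.** The protocol says that it works backward from the number of completers, and it defines dropout among those who start. Together these fix the calculation: divide the completers by the proportion expected to finish. The stated 10 does not come from that division. It comes from adding 25% of the completers to the completers, which is a different and smaller allowance.

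What is at stake is whether the plan has the protection it claims. Section 11.2 calls the allowance conservative, and section 16.1 treats 8 completers as required. If 25% really is the recent experience, the plan expects to finish with fewer than 8. The extra participants mentioned in 12.5 and 16.1 do not make up the gap, because they are the same 2 people already counted in the 10.

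**Working it through.** **Inputs**

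- Completers needed: 8 (11.2, 16.1, 18.2).
- Dropout rate: 25%, applied to starters (11.2).
- Recruitment target: 10 (11.2).
- Replacements planned: at most 2 (12.5, 16.1), so planned starters are at most 8 + 2 = 10.

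**Reproducing the stated figure**

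8 × (1 + 0.25) = 10. Equivalently, 2 extra on a base of 8 is 2/8 = 25%. The 10 is therefore 25% of completers added on top.

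**Working backward as 11.2 describes**

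Starters = completers/(1 − dropout) = 8/(1 − 0.25) = 8/0.75 = 10.67, so 11.

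**Dropout that 10 starters can absorb**

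(10 − 8)/10 = 2/10 = 20%.

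**Expected completers**

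- 10 starters at 25%: 10 × 0.75 = 7.5.
- 11 starters at 25%: 11 × 0.75 = 8.25.
- 10 starters at 20%: 10 × 0.80 = 8.0.

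**Chance of at least 8 completers**

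This assumes that people drop out independently and at exactly the stated rate. The number of completers is then binomial.

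10 starters, 25% dropout:
45 × 0.75⁸ × 0.25² + 10 × 0.75⁹ × 0.25 + 0.75¹⁰ = 0.2816 + 0.1877 + 0.0563 = 0.526.

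Starting 8 and replacing up to 2 in turn gives the same probability, since both succeed exactly when no more than 2 of 10 are lost.

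| Starters | Dropout | Expected completers | P(at least 8) |
|---|---|---|---|
| 10 | 25% | 7.5 | 52.6% |
| 11 | 25% | 8.25 | 71.3% |
| 12 | 25% | 9.0 | 84.2% |
| 10 | 20% | 8.0 | 67.8% |

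**What the slip itself costs**

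71.3% − 52.6% = 18.7 percentage points, about 19, from one participant fewer.

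**The case against.** The best defence is that 25% was meant as 2 extra on a base of 8, so that 10 is simply 8 plus a quarter. That explains the figure but does not rescue the sentence. Section 11.2 says it works backward and counts dropouts among those who start, and on that basis 2 lost of 10 is 20%.

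A second objection is that 10 may not be a firm limit. Section 11.2 says elsewhere that people who withdraw will be replaced, without a cap in that sentence, and the closing words of the rule in 12.5 are loose. This stands to a small degree, so 10 is best called the planned maximum. Still, 11.2, 12.5 and 16.1 all arrive at 8 plus 2, and none provides for an eleventh starter.

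A third objection concerns size, and most of it stands. A reader might take the whole 47% risk of missing 8 as the price of the error. It is not. Eleven starters would still miss 8 about 29% of the time, because inflating to an expected value never guarantees the target. A dropout is also not always a total loss. Someone who finishes two treatments stays in the full analysis set, and section 18.5.3 has the mixed model treat incomplete sequences as missing at random. Only the per-protocol set loses every non-completer.

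A reader might also infer that 7 completers would bring a known fall in power, or that the calculation in 18.2 has no slack. The protocol does not support either. Section 18.2 calls 1.53 g a standard error derived from a p-value and does not give the cited study's design or size. For a 2.2 g difference with 8 participants, paired-t power is about 70% if 1.53 g is taken as a within-person SD and 93% if it is taken as the SD of the paired difference. Both readings are assumptions, so no power loss can be quoted. The 7 g contrast in the same section is also far larger than 2.2 g.

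**Conclusion.** The sentence in 11.2 is wrong as written. At the protocol's own dropout rate and definition, 8 completers need 11 starters. The planned maximum of 10 covers 20%, and calling it conservative is not justified when 10 starters at 25% are expected to yield 7.5 completers and reach 8 only about 53% of the time.

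The consequence is modest: one participant, and about 19 percentage points in the chance of reaching 8. It bears mainly on the per-protocol set. The 11, the 20% and the 7.5 are plain arithmetic. The probabilities rest on independent dropout at exactly the assumed rate. Nothing here shows that the analysis is invalid, and the size of any power loss cannot be established from this document.

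**What to change.** Correct section 11.2 in one of two ways, and delete the word conservative in either case.

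- If 20% is an acceptable planning rate, say that a maximum of 10 recruits allows for 20% dropout among those who start.
- If 25% is the true experience, keep it and say that 10 recruits give 7.5 expected completers.

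The cost is one corrected sentence, with no change to design, analysis or recruitment. Either wording makes the plan accurate, but neither raises the chance of reaching 8. Even at 20% dropout, 10 starters fall short about 32% of the time.

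If the sponsor wants 25% actually covered in expectation, the target becomes 11. The replacement limit in 12.5 and the contingency in 16.1 would then have to move from 2 to 3 to match. That costs one more participant with three study visits.

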12 STUDY POPULATION

12.1 Description

8 healthy older male and female participants (67-77 years of age; BMI ≥ 23 to ≤ 30 kg/m²). Further definition is provided within the inclusion/exclusion criteria sections 12.3 and 12.4.

12.2 Subject screening

Participants recruited will be individually screened via interview to establish availability and electability.

12.3 Subject inclusion criteria

All participants must comply with the following inclusion criteria:

- Men and women aged 67 to 77.
- BMI: ≥ 23 and ≤ 30
- HbA1c within the non-diabetic or pre-diabetic range of < 40 mmol/mol.
- Sedentary to moderate physical activity.
- Obtained his/her informed consent.

12.4 Subject exclusion criteria

Participants representing one or more of the following criteria are excluded from participation in the study:

- Planning on leaving the city or proximity to participate in all 3 study arms for the entire study duration, or any other foreseen factor that may prevent completion of the study.
- Other foreseen factors that may prevent the completion of the study.
- Criteria-defined sedentary due to a precluding disability.
- Missing hands (for arterialized-venous blood sampling)
- Active malignancy (cancer) within the past six months.
- Unwilling to ingest meat alternatives.
- Allergy to experimental foods (i.e., gluten, lectin, and allergens).
- Any gastrointestinal disease or disorder that may affect the study outcomes.
- Gastrointestinal bypass surgery or congenital gastrointestinal issues.
- Chronic inflammatory disease (rheumatoid arthritis, psoriasis, psoriatic arthritis, Crohn's disease, ulcerative colitis, and ankylosing spondylitis).
- Taking supplements or medications that are thought to interfere with the study outcomes.
- Physical activity level (PAL) > 2.25 (below vigorous physical activity).
- Currently participating or having participated in another clinical study during the last four weeks prior to the beginning of this study that may affect results.

12.5 Subject withdrawal criteria

The study participants are entitled to withdraw from the study at any time voluntarily and for any other reason without affecting their access to the treatment or their future treatment by the Investigator. In addition, a participant may be withdrawn from the study at any time for reasons including, but not limited to, the following:

- Investigator's medical decision when continuing the study would compromise the safety of the participant.
- The participant is unwilling or unable to adhere to protocol requirements.
- In the event of injury.
- Non-compliance with the dietary intervention protocols (pre-intervention control diet and interventional diet).
- Observation of adverse effects.
- Absence from more than two testing sessions.

Participants will be notified by the Investigator prior to withdrawal from the study/investigational product in writing with a full explanation for their withdrawal. Depending on the time of withdrawal from the study protocol, participants will be followed up as follows:

- Prior to or following participation in any trials, participants will be provided standard notification of reasons for withdrawal.
-

- During the trials, participants will be withdrawn following non-compliance to the interventional diets, inability to maintain a normal diet and allowed physical activity patterns, or any observed adverse effect. Participants' condition will be monitored for 24 hours following withdrawal if due to adverse effects.

Participants withdrawn during the study will be replaced in randomized sequence order until n=8 is complete or a maximum dropout replacement of 2 is met or exceeded.

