8 STUDY PLAN OVERVIEW

Days		1	8	15
		↑	↑	↑
Visits	0	1	2	3
	Recruitment	Test days		

Study plan showing the four visits to the lab. Days 1 through 15 assume weekly testing for men and women.

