16.6 Follow-up

Following the completion of the study, each participant will be given a contact number at Massey University, where they can contact a member of the experimental team should any adverse effects develop.

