19.7 Follow up

All SAEs must be followed up until the SAE outcome is known.

A follow-up visit may be required if an SAE(s) persist beyond study termination. Further analyses are required to evaluate a potential cause-effect relationship between the study and the adverse event. In that case, all examinations, laboratory analyses, and their results will be documented in the case report forms or an attached file. Any SAE occurring within 30 days after the last study product intake will be similarly reported within 24 hours.

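### Sections 12.5 and 19.7 are not reconciled for a withdrawal caused by an SAE, and no scheduled contact covers the protocol's own 30-day SAE reporting window

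*Protocol*

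**What the plan says.** - Section 12.5 describes how withdrawn participants are followed up, according to when they withdraw. For withdrawal during the trials, the safety element is one sentence: "Participants' condition will be monitored for 24 hours following withdrawal if due to adverse effects". For withdrawal before or after taking part in any trial, it mentions only notification of the reasons.
- Section 19.7 deals with SAEs. On duration: "All SAEs must be followed up until the SAE outcome is known". On the period after the last meal: "Any SAE occurring within 30 days after the last study product intake will be similarly reported within 24 hours". It also allows for a further visit: "A follow-up visit may be required if an SAE(s) persist beyond study termination".
- Section 16.6 is the only general provision for contact after the study. Once the study is complete, participants receive a number to call, through which "they can contact a member of the experimental team should any adverse effects develop".
- Section 8 fixes the calendar: "Study plan showing the four visits to the lab. Days 1 through 15 assume weekly testing for men and women". The test days are days 1, 8 and 15, and nothing is scheduled later.
- Section 19.6 starts the 24-hour SAE entry clock when the event becomes known to the study team.

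**The concern.** Section 12.5 gives a fixed 24 hours for withdrawal due to adverse effects of any severity, serious ones included. Section 19.7 gives an open-ended duration for SAEs. Staff working from 12.5 alone would find no pointer to the longer obligation, and the participants concerned are those already known to have reacted.

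Separately, the protocol commits itself to reporting SAEs over 30 days but schedules nobody to ask about them in that time. Participants are aged 67 to 77. Each test day involves two catheters, a 5.5-hour infusion and about 140 mL of blood. An effect of Visit 1 or 2 can come to light when the participant returns about a week later. An effect of Visit 3 has no such return visit. If the report then says that no SAE occurred within 30 days, that statement rests on participants having chosen to call.

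**Working it through.** The protocol states no figure that can be reproduced here. The check is a comparison of the sections plus calendar arithmetic.

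**1. Scope of the two rules**

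| | Section 12.5 | Section 19.7 |
|---|---|---|
| Who | Participants withdrawn because of adverse effects | Any participant with an SAE |
| Which events | Adverse effects of any severity | SAEs only |
| Duration | 24 hours of monitoring | Until the outcome is known |
| Reporting window | None stated | 30 days after the last intake |
| Reference to the other section | None | None |

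The 30 days is a period within which an SAE must be reported. It is not a length of follow-up, so it should not be set against the 24 hours as a rival duration. The rules meet only where an SAE causes withdrawal. There, 12.5 names 24 hours and 19.7 names the outcome as the end point. A site can do both, but the text does not say that it must.

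**2. Calendar**

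Inputs: test days 1, 8 and 15 (section 8), a 30-day window after the last intake (19.7), and 24 hours of monitoring (12.5). End of window = day of last intake + 30. The withdrawal rows assume withdrawal for an adverse effect on the test day itself.

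| Participant | Last intake | End of window | Planned active contact in the window |
|---|---|---|---|
| Completer | day 15 | 15 + 30 = day 45 | none |
| Withdrawn at Visit 1 | day 1 | 1 + 30 = day 31 | 24 hours, then 30 − 1 = 29 days with none |
| Withdrawn at Visit 2 | day 8 | 8 + 30 = day 38 | 24 hours, then 30 − 1 = 29 days with none |

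Seven days is the minimum washout. Longer gaps move the day numbers but add no scheduled contact after the last intake.

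**3. How a new SAE in the window could become known**

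- *Contact number (16.6).* The participant has to start the contact. The number is described as given after study completion, and withdrawn participants are not mentioned.
- *Possible follow-up visit (19.7).* It depends on an SAE that is already known and persists, so it cannot detect a new one.
- *24-hour entry rule (19.6).* It runs from knowledge of the event. An event that nobody volunteers never starts the clock.

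For a new event after the last planned contact, the only route described is self-report. The protocol gives no event rate, so the number of events that might be missed cannot be computed.

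**The case against.** The strongest reply is that nothing here conflicts. One rule is short monitoring after withdrawal for any adverse effect, however mild; the other is outcome follow-up for SAEs, with no exception for withdrawn participants. Section 12.5 nowhere says that SAE follow-up or reporting ends at 24 hours. This stands. A reader might infer that the two sections contradict each other, or that a site following 12.5 closes the case after a day. The documents do not support either inference.

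A reader might also infer that no contact at all is planned after the last visit, or that the 30-day window cannot be filled. Both go too far. Section 16.6 provides a number to call, 19.7 allows a visit for a persisting SAE, and reporting from knowledge is consistent with participant reports. What remains is that capture depends on self-report and may be incomplete.

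It is tempting to express the gap as a share of days, such as 1 of 30 or 30 of 45. The first divides a monitoring period for any adverse effect by an SAE reporting window. The second implies that days 1 to 15 are covered throughout, when only three of them are test visits. Neither measures missed events.

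Nor is there a case for bias between meals. Sections 10.2, 10.4 and 18.1 name no safety outcome or safety comparison, and sequences are randomly assigned on a Youden square, so the last meal is not systematically one of the three.

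Finally, consent and contact pages are not among the material reviewed. Participants may receive a number earlier than 16.6 says, so its absence before completion cannot be claimed.

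**Conclusion.** The point holds as a cheap improvement to safety ascertainment. Two gaps are supported by the text. First, 12.5 and 19.7 overlap without reference to each other when an SAE causes withdrawal. Second, the protocol describes no active means of finding SAEs in its own 30-day reporting window: there are no scheduled contacts after Visit 3 for completers, and none after the 24 hours for participants withdrawn because of an adverse effect.

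This rests on the schedule in section 8 being complete and on no follow-up contact being set out in material not seen. No judgement is made on which follow-up duration is right. The efficacy results do not depend on this point.

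**What to change.** 1. Reconcile section 12.5 with section 19.7 for withdrawals due to adverse effects, with a cross-reference in each. The sponsor decides which rule governs.
2. Add to section 16.6 one brief scheduled adverse-event enquiry, by telephone or e-mail, at the end of the 30-day window already stated in 19.7. It should cover every participant, completed or withdrawn, with the date and answer recorded even when there is nothing to report.
3. State in section 16.6 that the contact arrangement applies to withdrawn participants too.

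The cost is a wording change and one short contact for each of 8 to 10 people. A few more minor events will probably be recorded. No extra visit, sample or analysis is needed.
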